## 2 Introduction

This Statistical Analysis Plan (SAP) describes the planned analysis and reporting for Sobi protocol NI-0501-08 (An observational, multicenter study to evaluate levels of Interferon gamma (IFN $\gamma$ ) and other inflammatory mediators in Adult Patients with Hemophagocytic Lymphohistiocytosis (A-HLH)).

The present observational study is designed to provide a better understanding of IFN $\gamma$  and IFN $\gamma$  inducible chemokines as markers of HLH disease activity in adults, and of the potential of IFN $\gamma$  to represent a therapeutic target in this patient population.

Adult patients ( $\geq 18$  years old) are eligible, if having consented to the use of their clinical data for research purposes. Clinical data and sample collection may be performed either retrospectively (provided that sufficient clinical information is available to allow for a meaningful interpretation of the biomarker results) and prospectively.

If retrospective cases are evaluated, the presence of a malignancy and the diagnosis of primary HLH (defined as homozygous mutation in a known HLH causative gene) represent exclusion criteria for the study. On the contrary, if prospective patients are considered, inclusion in the study may occur before the diagnostic work-up has been completed. In case the diagnosis of malignancy-related HLH or primary HLH (as above defined) is made, the data collected will be analyzed separately.

The purpose of this SAP is to outline the exploratory analyses to be completed to support the synopsis for protocol NI-0501-08. Any post-hoc analyses not identified in this SAP will be clearly identified as such in the synopsis. The exploratory analyses identified in this SAP could be included in regulatory submissions and/or future manuscripts. Also, additional exploratory analyses not necessarily identified in this SAP may be performed to support the clinical development program.

The structure and content of this SAP provides sufficient detail to meet the requirements identified by the FDA and International Conference on Harmonisation of Technical Requirements for Registration of Pharmaceuticals for Human Use (ICH): Guidance on Statistical Principles in Clinical Trials. All work planned and reported for this SAP will follow internationally accepted guidelines, published by the American Statistical Association and the Royal Statistical Society, for statistical practice.

### 3 Study objectives and endpoints

#### 3.1 Study objectives

- To determine the levels of inflammatory markers including, but not limited to interferon gamma (IFN $\gamma$ ), interleukin 1 beta (IL1 $\beta$ ), interleukin 6 (IL-6), interleukin 10 (IL-10), interleukin 17 (IL-17), interleukin 18 (IL-18), soluble IL-2 Receptor  $\alpha$  (sCD25), C-X-C chemokine ligand 9 (CXCL9), C-X-C chemokine ligand 10 (CXCL10), C-X-C chemokine ligand 11 (CXCL11), soluble CD163 (sCD163), neopterin and Tumor Necrosis Factor alpha (TNF $\alpha$ ) in adult patients diagnosed with A-HLH and whenever possible, to monitor the evolution over time of these markers.
- To assess the relationship between the above-mentioned inflammatory cytokines and disease activity.
- To explore the presence of genetic variants of the genes typically causing primary HLH in these patients and any association with the course of the HLH disease.

#### 3.2 Study endpoints

##### 3.2.1 Inflammatory biomarkers

Level of

Confidential

Version 1.0

Page 5 of 14

- CXCL10 (pg/mL )
- CXCL9 (pg/mL )
- IFN $\gamma$  V-PLEX (pg/mL )
- IL10 V-PLEX (pg/mL )
- IL1B V-PLEX (pg/mL )
- IL6 V-PLEX (pg/mL )
- Neopterin (nM )
- TNFa V-PLEX (pg/mL )
- Total hIFN $\gamma$  (pg/mL )
- sCD163 (ng/mL )
- sIL2R $\alpha$  (pg/mL ), also called sCD25

Note: No data reported for C-XC chemokine ligand 11 (CXCL11), interleukin 17 (IL-17) and interleukin 18 (IL-18).

### 3.2.2 Inflammatory biomarkers- correlation

The degree of correlations between inflammatory markers and between selected inflammatory markers and markers of disease activity (lab assessments) will be investigated.

The inflammatory biomarkers are as listed in section 3.2.1 and the other laboratory assessments as defined in the protocol are listed below

- Albumin
- AST, ALT, Alkaline Phosphatase
- Basophils
- $\beta$ 2-microglobulin
- Total and conjugated Bilirubin
- BUN, serum creatinine
- CRP
- D-dimers
- Hemoglobin, Hematocrit, Red blood cells, white blood cells and differential count, platelets
- Fasting triglycerides
- Ferritin
- Fibrinogen
- Lactate dehydrogenase
- NK cell activity
- PT and aPTT
- Serum IgG
- Sodium

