Data collection may be performed retrospectively if sufficient clinical information is available to allow for a meaningful interpretation of the biomarker results.

For biomarker analysis, a maximum of 5 ml of whole blood will be required per time point. Details on sample processing and shipment will be described in a separate brief laboratory manual provided to the site. Whenever possible, serum (and not plasma) should be obtained for shipment, as this is the preferred matrix for the biomarker analysis.

Relevant clinical information gathered by the treating physician will be collected in a data collection form. This will include information on the clinical presentation of HLH, the assessments performed to characterize the secondary form, in particular those for identification of the potential HLH trigger, the date of onset of the background disease (if any) in relation to HLH manifestations, treatment regimen prior to and/or ongoing at the time of HLH onset, clinical and laboratory parameters relevant to HLH, specific HLH therapy with best response to the therapy, other concomitant medications, patient follow-up and disposition, stem cell transplant status, duration of response, and survival. As appropriate, collection of serum samples for biomarker analysis and relevant information should occur at HLH diagnosis, and at regular time intervals during the treatment course (not more than once a week) up to resolution of HLH.

If patients present CNS involvement and lumbar puncture is being performed for diagnostic or therapeutic purposes, a CSF sample will be collected, if possible, for biomarker assessment, in particular CXCL9 and CXCL10.

If feasible and consistent with the standard clinical practice at the site, genetic characterization will be performed. A specific consent for genetic testing must be given by the patient. Genetic samples

CONFIDENTIAL

may also be collected from existing bank of samples (frozen whole blood in EDTA or frozen extracted DNA), if the patient's consent has been previously obtained.

Medical history, in particular all available information on search conducted for the identification of the potential HLH trigger needs to be collected.

Study Duration: This study will gather information on adult HLH patients at diagnosis and, as available, during treatment of the disease up to HLH resolution, and will last until completion of the planned recruitment.

Parameters:

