- 1. Laboratory parameters**, at the time of HLH diagnosis, to be assessed at the site laboratory, such as:
 - Hemoglobin, Hematocrit, red blood cells, white blood cells and differential count, platelets
 - Fibrinogen
 - Ferritin
 - Fasting triglycerides
 - AST, ALT, Alkaline Phosphatase
 - BUN, serum creatinine
 - Albumin
 - Sodium (if available)
 - Beta2 microglobulin (if available)
 - Serum IgG levels (if available)
 - Lactate dehydrogenase
 - Total and conjugated Bilirubin
 - D-dimers
 - PT, aPTT
 - CRP
 - Functional tests, such as perforin expression and NK-cell activity (if performed)

Results of additional tests performed for the patient's follow-up at regular time intervals during the treatment course (not more than once a week) up to resolution of HLH will be recorded, as available.

CONFIDENTIAL

2. Other relevant parameters, at the time of sample collection, in particular body temperature, spleen and liver size (if available), findings in bone marrow biopsy.

3. Inflammatory markers of disease activity. The following assessments will include but not be limited to:

- IFN γ
- sCD25
- IL-1 β , IL-6, IL-10, IL-17 IL-18
- TNF α
- CXCL9, CXCL10, CXCL11
- sCD163 and neopterin

These tests will be performed at Novimmune Bioanalytical Laboratory and results will be made available to the patient's treating physician and to the patient.

4. Medical history, in particular any available additional information on the background disease considered to be the potential trigger of HLH, e.g.:

- Infections (including viral load, bacterial and/or fungal search)
- Rheumatologic diseases

Statistical Analysis:

All analyses are exploratory. Statistical analyses of the data collected in this study will be focused on providing tabular and graphical summaries of the levels of inflammatory markers and of the clinical features of the disease both at diagnosis and during the course of treatment. The degree of correlation between inflammatory markers, and between inflammatory markers and the severity of clinical manifestations, response to therapy, and survival of the patients will be assessed. Analyses may also be performed to study these relationships in various subgroups of patients, depending on the demographic, genetic and clinical characteristics observed (notably, HLH of unknown origin representing a specific subgroup of interest).

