### **13.2 Inflammatory biomarkers - correlations**

The degree of correlations between inflammatory markers and between inflammatory markers and laboratory assessments (potential markers of disease activity) will be assessed.

The correlations to be performed are:

1. All inflammatory biomarkers vs. all other inflammatory biomarkers as listed in section 3.2.1
2. Biomarkers relevant for emapalumab (i.e. CXCL9, CXCL10, IFN $\gamma$  and sIL2R $\alpha$ ) vs. all laboratory assessments as listed in section 3.2.2

The correlations will be evaluated by plotting biomarker scores i.e., CXCL9 vs. CXCL10 (for all combinations) in scatter plots. The biomarker value closest to the date of HLH diagnosis will be used if more than one sample available. A-HLH and M-HLH patients will be shown in the plots with different colours or symbols.

Data will be investigated to confirm normal or log-normal distribution of the parameters. If normal, the actual values will be plotted. If not normal, log-transformed values will be plotted.

The correlated samples should be within a time frame of three days.

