## 14.3 Vital signs

Weight and Height are only collected at screening/ICF. They will be presented as part of the Demographic table (see Section 10.1).

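### The SAP relates the markers to laboratory tests only, and does not declare that the protocol's correlation with clinical severity has been dropped

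*SAP*

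**What the plan says.** **Protocol.** The second study objective is to relate the inflammatory markers to disease activity. The Statistical Analysis section says that the degree of correlation "between inflammatory markers and the severity of clinical manifestations, response to therapy, and survival of the patients will be assessed". Item 2 of the Parameters section lists what else is to be recorded when a sample is taken: "in particular body temperature, spleen and liver size (if available), findings in bone marrow biopsy". CNS involvement enters under Study Design and Procedures, as the condition for an extra sample: "If patients present CNS involvement and lumbar puncture is being performed for diagnostic or therapeutic purposes, a CSF sample will be collected", if possible.

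**SAP.** Section 3.1 repeats the objective. Section 3.2.2 then speaks of correlation between selected markers and "markers of disease activity (lab assessments) will be investigated". Section 13.2 says that correlation between the markers and "laboratory assessments (potential markers of disease activity) will be assessed", and lists the correlations to be done:

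- every marker against every other marker;
- CXCL9, CXCL10, IFNγ and sIL2Rα against the laboratory tests of 3.2.2.

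Fever, splenomegaly and CNS involvement appear in SAP 10.2 as medical-history items, summarised and listed by A-HLH and M-HLH. Section 13.4 has no subgroup other than A-HLH and M-HLH. Section 15 declares two changes from the protocol: no data for CXCL11, IL-17 and IL-18, and no genetic analysis.

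**The concern.** The protocol names clinical severity as one of the things the markers will be set against. The SAP keeps the objective but treats disease activity as a set of laboratory tests. If the SAP is followed as written, the report will contain no display linking a marker to a clinical sign.

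Two things are at stake. First, the study's stated purpose is to understand IFNγ and its chemokines as markers of HLH activity in adults, and the clinical part of that question would go unexamined. The protocol's background already reports that these markers correlated with ferritin, platelets and transaminases in other HLH groups, so laboratory plots mainly extend a known pattern to adults. Second, SAP Section 2 allows these analyses to go into regulatory submissions or manuscripts. Because Section 15 does list other dropped analyses, a reader would assume that the remaining protocol correlations were carried out, and could take a laboratory result as evidence on disease activity in general.

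**Working it through.** The plan gives no figure to reproduce: there is no sample size calculation, and SAP Section 8 presents no tests. The check is a comparison of the two texts and a count of the planned displays.

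**Inputs**

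- Marker assays in SAP 3.2.1: 11.
- Laboratory tests in SAP 3.2.2: 27, counting the differential as one item and basophils separately (26 if basophils are counted within the differential).
- Markers carried into the laboratory comparison in SAP 13.2: 4 (5 if both IFNγ assays are used).
- Patients in SAP Sections 6 and 8: 14, of whom 4 are M-HLH, leaving 14 − 4 = 10 A-HLH.

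**Count of planned pairings**

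| Comparison | Calculation | Pairs |
|---|---|---|
| Marker with marker | 11 × 10 / 2 | 55 |
| Marker with laboratory test | 4 × 27 | 108 (5 × 27 = 135 with both IFNγ assays) |
| Marker with fever, temperature, spleen, liver or CNS involvement | none listed | 0 |

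The same protocol sentence also names response to therapy and survival. Section 13.2 lists no pairing with these either; SAP Section 11 only summarises outcome.

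**Where each clinical item stands**

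| Item | Protocol | SAP |
|---|---|---|
| Fever | Body temperature at sampling (Parameters, item 2) | Among the HLH criteria in 10.2; temperature as a measurement is absent |
| Spleen | Size at sampling, if available | Splenomegaly among the HLH criteria in 10.2; size absent |
| Liver | Size at sampling, if available | Absent, including hepatomegaly |
| CNS involvement | Condition for CSF sampling | Medical-history item in 10.2 |

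Three items (fever, splenomegaly, CNS involvement) therefore have a field that the SAP already uses. Temperature and organ size do not, and the SAP does not show whether they were captured. Section 14.3, headed Vital signs, says only that "Weight and Height are only collected at screening/ICF" and does not mention temperature.

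**How much of disease activity the laboratory panel covers.** SAP 10.2 lists eight HLH criteria. Five have an underlying measure in the planned plots: cytopenias, triglycerides/fibrinogen, ferritin, sIL-2R and NK activity. Three do not: fever, splenomegaly and hemophagocytosis in bone marrow.

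**Does other wording restore the analysis?** SAP 5.2 refers to final analyses identified in the protocol, and SAP Section 2 allows further exploratory analyses. Neither specifies a display of a marker against a clinical sign, and the list in 13.2 is written as complete.

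**The case against.** The strongest reply is that laboratory tests are a proper measure of HLH activity. The protocol's background itself calls ferritin, platelet count and transaminases measures of severity, and five of the eight criteria in SAP 10.2 are represented in the planned plots. That stands. A reader might infer that the objective is answered only by setting markers against one another, but four markers are plotted against the site laboratory panel, so the SAP's choice is incomplete rather than wrong. Nor is there ground for criticising sodium, BUN or basophils as unspecific. Sodium and BUN are in the protocol's list, basophils belong to its differential count, and the documents say nothing about their specificity.

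A second reply is that the clinical data may not exist. This stands in part. Retrospective cases are allowed without limit, organ size is recorded only if available, and the SAP shows no temperature field. It does not apply to fever, splenomegaly and CNS involvement.

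A third reply is that plots by presence or absence do not show severity and are poorly matched in time. Fever and splenomegaly in 10.2 are diagnostic criteria, while SAP 13.1 requires the marker value to come after diagnosis. That is a real limit on what the plots can show, and must be stated with them.

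A fourth reply is that the study is small and exploratory, and every patient's data will be listed, so a reader could make the comparison by hand. True, but the SAP plots more than 100 pairings on the same 14 patients, and listings do not replace an analysis the protocol said would be done.

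**Conclusion.** The point holds as an undeclared narrowing of a protocol analysis. The protocol commits to relating the markers to clinical severity, the SAP plans no such display, and Section 15 is silent. The marker-to-activity objective is answered for laboratory activity only. It should be corrected, but it does not undermine the planned laboratory analyses.

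Two stronger readings are not supported. One is that clinical signs were recorded with every sample for all 14 patients and then ignored: the protocol qualifies organ size, and the SAP shows fields only for fever, splenomegaly and CNS involvement. The other is that the protocol promised correlation with those particular signs: its sentence refers to clinical manifestations in general and names none. The individual signs come from its parameter list and from the CSF sampling text.

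The conclusion assumes that the fields named in SAP 10.2 are filled in for enough patients to plot. How many is not stated.

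**What to change.** 1. **SAP 13.2:** add dot plots of CXCL9, CXCL10, IFNγ and sIL2Rα by fever, splenomegaly and CNS involvement (yes/no, from the 10.2 fields). Use the marker value closest to HLH diagnosis, show n in each group, exclude missing values, and keep the A-HLH and M-HLH symbols. State that the plots show presence at diagnosis, not graded severity. This is 4 × 3 = 12 panels.
2. **If body temperature or spleen or liver size was recorded with the marker sample:** add scatter plots of the same four markers under the existing three-day window.
3. **SAP 3.2.2:** change the parenthesis so that it covers the clinical items as well as the laboratory ones.
4. **SAP Section 15:** declare every clinical correlation in the protocol that cannot be done, and for that part limit the conclusion to laboratory markers of activity.

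The cost is SAP wording and a few plots from data already held. Groups will be very small: in a yes/no split the smaller group has at most 5 of 10 A-HLH patients and at most 2 of 4 M-HLH patients, so the plots are descriptive only. If the database has already been locked, SAP 5.2 requires analyses not identified in the SAP to be labelled post hoc.

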### **3.2.3 Genetic variants**

Genetic data was obtained for 8 out of 14 patients, of these 4 had no known HLH mutation and the other 4 had mutations but none of them were diagnosed with pHLH. No analysis of genetic variants will be performed.

## **4 Study methods**

### **4.1 Overall study design and plan**

This is a non-interventional study designed to determine the levels of pro-inflammatory markers (as listed above) in adult patients diagnosed with HLH and to assess the relationship between the biomarkers and disease activity. Whenever possible, the evolution of inflammatory markers will be followed during HLH treatment and the relationship with the disease outcome explored.

Data collection may be performed retrospectively if sufficient clinical information is available to allow for a meaningful interpretation of the biomarker results.

Relevant clinical information gathered by the treating physician will be collected in a data collection form. This will include information on the clinical presentation of HLH, the assessments performed to characterize the secondary form, in particular those for identification of the potential HLH trigger, the date of onset of the background disease (if any) in relation to HLH manifestations, treatment regimen prior to and/or ongoing at the time of HLH onset, clinical and laboratory parameters relevant to HLH, specific HLH therapy with best response to the therapy, other concomitant medications, patient follow-up and disposition, stem cell transplant status, duration of response, and survival.

As appropriate, collection of serum samples for biomarker analysis and relevant information should occur at HLH diagnosis, and at regular time intervals during the treatment course (not more than once a week) up to resolution of HLH. If patients present CNS involvement and lumbar puncture is being performed for diagnostic or therapeutic purposes, a CSF sample will be collected, if possible, for biomarker assessment, in particular CXCL9 and CXCL10.

If feasible and consistent with the standard clinical practice at the site, genetic characterization will be performed. A specific consent for genetic testing must be given by the patient. Genetic samples may also be collected from existing bank of samples (frozen whole blood in EDTA or frozen extracted DNA), if the patient's consent has been previously obtained.

Medical history, in particular all available information on search conducted for the identification of the potential HLH trigger needs to be collected.

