## 11 HLH outcome

HLH outcome will be summarized for the All enrolled set and split by A-HLH and M-HLH groups and will include:

- HLH resolved (Yes/no)

- HLH reactivated (Yes/no)
- Has HSCT been performed (Yes/no)
- Is patient alive (Yes/no)

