## 13 Endpoint analyses

### 13.1 Inflammatory biomarkers

The inflammatory biomarkers as listed in section 3.2.1 will be displayed in scatter plots and split by A-HLH and M-HLH groups as in the below example.

If several samples available the biomarker value closest to the date of HLH diagnosis (value must be after HLH diagnosis) will be used.

Biomarker data will be summarized for all patients by A-HLH and M-HLH groups using descriptive statistics.

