## 14.2 Laboratory data

A subset of the laboratory data collected will be displayed in scatter plots the same way as the biomarker data described in section 13.1. The lab data to be plotted are:

- AST, ALT, Alkaline Phosphatase
- Total and conjugated Bilirubin
- CRP
- D-dimers
- white blood cells and differential count, platelets
- Ferritin
- Fibrinogen
- Lactate dehydrogenase

The value closest to the date of HLH diagnosis (value must be after HLH diagnosis) will be used if more than one sample is available.

Laboratory data will be summarized by A-HLH and M-HLH groups using descriptive statistics.

All laboratory data will be listed by patient.

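### The SAP plans no analysis of biomarkers over time or against response or survival, all of which the protocol commits to, and Section 15 does not list them as dropped

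*SAP*

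**What the plan says.** The protocol's Statistical Analysis text makes two commitments that matter here, neither with a proviso about feasibility. One is to tables and graphs, described as "summaries of the levels of inflammatory markers and of the clinical features of the disease both at diagnosis and during the course of treatment". Another concerns correlation: "between inflammatory markers and the severity of clinical manifestations, response to therapy, and survival of the patients will be assessed".

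The SAP keeps these as aims in softer form. Section 3.1 has the objective, "whenever possible, to monitor the evolution over time of these markers". Section 4.1 repeats the protocol's design statement: "Whenever possible, the evolution of inflammatory markers will be followed during HLH treatment and the relationship with the disease outcome explored".

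The analysis sections reduce repeat samples to one:

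- Section 13.1 (biomarker plots): "If several samples available the biomarker value closest to the date of HLH diagnosis (value must be after HLH diagnosis) will be used".
- Section 13.2 (correlations): "The biomarker value closest to the date of HLH diagnosis will be used if more than one sample available".
- Section 14.2 (laboratory plots) likewise takes the value nearest to and after diagnosis, which "will be used if more than one sample is available".

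The descriptive summary in Section 13.1 is by A-HLH and M-HLH group and names no time point. Section 11 tabulates resolution, reactivation, transplant and vital status by the same two groups, with no biomarker. Section 13.4 has only the A-HLH/M-HLH split. Section 15 lists two changes from the protocol: no analysis of CXCL11, IL-17 and IL-18, and none of genetic variants.

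**The concern.** The study is meant to show whether IFNγ and the chemokines it induces track disease activity in adults, and whether IFNγ is a plausible therapeutic target. How markers move under treatment, and how they relate to response and survival, bear directly on that. If the SAP is followed exactly, these questions get no planned display.

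The record is also at stake. Section 15 is where a reader looks for departures from the protocol. Because the genetic analysis and the three unreported markers are declared there, a reader would take everything else to have been kept. Under SAP Sections 2 and 5.2, an analysis that the SAP does not identify must be labelled post hoc if it appears in the synopsis. The time-course and outcome analyses would then carry that label although the protocol planned them. Section 2 also allows for use of the SAP's analyses in regulatory submissions and manuscripts, so the list of changes should be complete.

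**Working it through.** The documents give no figure to reproduce here: SAP Section 6 states that there was no formal sample size calculation. The check sets each protocol commitment against the SAP.

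| Protocol commitment | Kept among SAP aims | Planned SAP analysis | Declared in Section 15 |
|---|---|---|---|
| Marker levels during treatment | 3.1 and 4.1, where possible | None by time | No |
| Markers against response | 4.1 (outcome), where possible | None | No |
| Markers against survival | 4.1 (outcome), where possible | None; vital status tabulated alone in 11 | No |
| Markers against severity | 3.1 (disease activity) | 13.2, through laboratory tests | Not needed for that part |
| Markers against each other | 3.2.2 | 13.2, all pairs | Not needed |
| CXCL11, IL-17, IL-18 | 3.1 | None (3.2.1) | Yes |
| Genetic variants | 3.1 | None (3.2.3, 13.3) | Yes |

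**Count.** Section 3.2.1 lists 11 biomarker measures, two of them IFNγ assays. Of these, 0 have a planned summary or plot by time and 0 have a planned display against response or survival.

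**The Section 13.1 summary.** It does not restate the one-value rule. If the rule applies, repeat values are left out. If it does not, repeat values are pooled without a time axis. On either reading nothing is summarised by time, and repeat values are certain to appear only in the individual listings of Section 8.

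**Values per plot.** With 14 patients, 4 of them M-HLH (Section 6), A-HLH has 14 − 4 = 10. Each biomarker therefore contributes at most 14 values to any one plot. Section 13.1 requires a value after diagnosis and Section 13.2 does not, so a patient could contribute a different value to each.

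**Share of measurements in no plot.** The number of repeat samples is not given. Assume an average of k samples per patient, with the same single value used throughout. The share is then 1 − 1/k:

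- k = 1: 0%
- k = 2: 1 − 1/2 = 50%
- k = 4: 1 − 1/4 = 75%

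The documents allow k = 1. Repeat sampling is as available and at most weekly, and retrospective cases are permitted. The range therefore starts at 0%.

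**Size of the outcome cells.** This bears on what the fix can deliver. Assume that the protocol's 40% to 75% overall adult mortality applies to the 10 A-HLH patients, so survival p runs from 0.25 to 0.60. Let X be the number alive, Binomial(10, p). The chance that the alive or the dead cell holds 0 or 1 patients is P(X ≤ 1) + P(X ≥ 9):

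- p = 0.60: 0.048
- p = 0.50: 22/1024 = 0.021, the lowest in the range
- p = 0.25: 0.244, the highest

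So there is a 2% to 24% chance that one cell is nearly empty.

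**The case against.** The strongest defence is that the SAP's aims are conditional on feasibility. All analyses are exploratory, no tests are presented, there are only 10 A-HLH patients, and every value is listed. Section 2 also leaves room for further exploratory analyses. Much of this stands. It limits the consequence and rules out anything beyond description.

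It does not remove the point. The proviso is attached to the objective and the design statement, not to the protocol's Statistical Analysis text. A listing is not the summary or correlation that was promised. Where the SAP found the data too thin, as for genetics, it said so and declared it in Section 15.

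Disease activity is partly covered, and that should be credited. Section 13.2 relates CXCL9, CXCL10, IFNγ and sIL2Rα to laboratory tests that include ferritin, platelets and transaminases, which the protocol's background treats as measures of severity. Response and survival are separate commitments.

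A reader might infer three stronger things that the documents do not support:

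- **That most measurements are discarded.** This needs an assumed number of repeat samples, and one sample per patient is possible.
- **That Section 5.2 keeps the protocol's analyses due.** Its sentence fixes only their timing, after database lock.
- **That the aims can be answered only by searching listings.** Section 2 permits additional exploratory analyses, though ones reported in the synopsis would be labelled post hoc.

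**Conclusion.** The point holds as a gap in coverage and an incomplete record of changes. Three analyses named in the protocol (marker levels during treatment, markers against response, markers against survival) have neither a planned SAP analysis nor an entry in Section 15. This affects all 11 biomarker measures. It rests on the text alone and needs no assumption about the data.

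The amount of data left undisplayed is unknown, and so is whether repeat samples or best response were recorded for enough patients to show anything. Best response is on the collection list in Section 4.1 but not among the Section 11 outcomes. No error rate or formal conclusion is affected. This should be fixed because the correction is small and the omission touches a stated objective.

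**What to change.** 1. **Section 15.** List, with the reason, each of the time-course, response and survival analyses that will not be done. If the data support none of them, this entry alone is enough.
2. **Section 13, where the data were collected.** Add the following as descriptive displays only, with n stated:
   - individual biomarker profiles against days from HLH diagnosis, for patients with at least 2 samples;
   - within A-HLH (n = 10), dot plots of the Section 13.1 value for the markers named in 13.2, by HLH resolved yes/no and alive yes/no, and by best response if recorded. Show days from diagnosis to sample and length of follow-up.

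**Cost.** SAP text, plus 11 profile panels and 4 markers (5 if both IFNγ assays count) × 2 outcomes = 8 to 10 dot plots, which makes 19 to 21 panels. With best response it is 11 + 12 to 15 = 23 to 26.

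**Limits to state with the displays.** Cells will be small. Section 13.1 sets no upper time limit, so a value may come from late in treatment. Section 11 gives vital status without follow-up time. Sampling stops at resolution, so the length of a profile depends on outcome. The displays can describe but cannot support inference.
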